- **Immunogenicity (anti-drug antibodies):** All protein therapeutics are potentially immunogenic. Because CSL312 is a protein, it has the potential to cause the development of ADAs. During the study, investigators will monitor subjects for the development of ADAs for clinical evaluation of any signs of immunogenicity.

Given the acceptable safety profile of CSL312 observed in the phase 1 study (CSL312_1001) and the two phase 2 studies (CSL312_2001 and CSL312_COVID-19), and taking into account the implementation of procedures in the current study to closely monitor subject safety, the associated benefit-risk assessment is considered to be acceptable. Additional information on CSL312 can be found in the CSL312 IB.

2 Study Objectives and Endpoints

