2.1.2 Primary Endpoints

Endpoints	Summary Measure
Subjects experiencing treatment-emergent adverse events (TEAEs) including: 
 • SAEs • AESIs • CSL312-induced ADAs • Clinically significant abnormalities in laboratory assessments that are reported as AEs 	Number and proportion of subjects experiencing the specified safety events after treatment with investigational product (CSL312 or placebo)

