10.3.3 Safety Analyses

TEAEs will be coded using the Medical Dictionary for Regulatory Activities (MedDRA) version 24.1 (or higher). A TEAE is defined as an AE reported at or after the start of the first administration of study treatment. Only TEAEs will be summarized.

An overview summary of TEAEs, including counts and percentages of subjects with any of the following events, will be produced:

- TEAEs
- TEAEs related to study treatment
- TEAEs leading to permanent discontinuation of study treatment
- Serious TEAEs
- Serious TEAEs related to study treatment
- Fatal TEAEs

- Fatal TEAEs related to study treatment
- TEAEs by severity
- Treatment-emergent AESIs

TEAEs will be summarized by system organ class and preferred term. TEAEs will also be summarized by causality and severity. All TEAE summaries will be provided for each treatment group and overall.

The number and percentage of subjects with plasma anti-CSL312 antibodies will be summarized by treatment group and overall.

Laboratory evaluations (hematology, biochemistry, and urinalysis) will be summarized descriptively by treatment group.

Change from Baseline in DL_{CO} will be summarized using descriptive statistics by treatment group.

The Safety Analysis Set will be used for the safety analyses unless indicated otherwise.

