4.1 Objectives and Endpoints

The primary objective of this study is to investigate the safety of CSL312 in subjects with IPF.

The secondary objectives of the study are:

1. To characterize the systemic PK of CSL312 in patients with IPF.
2. To investigate the PD activity of CSL312 in patients with IPF.

The exploratory objectives of the study are:

1. To investigate the potential effect of CSL312 on FXII-related pathways in patients with IPF.
2. To investigate the effect of CSL312 on lung function in patients with IPF.

Table 1 Study Objectives and Endpoints

Objectives	Endpoints and /or Estimand	Summary Measure(s)
Primary	Subjects experiencing treatment-emergent adverse events (TEAEs) including: 
 • Serious adverse events (SAEs) • Adverse events of special interest (AESIs [bleeding events, thromboembolic events (TEE), severe hypersensitivity]) • CSL312-induced antidrug antibodies (ADAs) • Clinically significant abnormalities in laboratory assessments that are reported as adverse events (AEs) 	Number and proportion of subjects experiencing the specified safety events after treatment with IP (CSL312 or placebo)
Secondary		
1	Plasma PK parameters after SC administration of CSL312 at each SC dosing interval: 
 • Trough plasma concentration (C_{trough}) • Maximum plasma concentration (C_{max}) (last SC dosing interval only) • Time to reach maximum plasma concentration (T_{max}) (last SC dosing interval only) • Area under the plasma concentration-time curve after the first dose interval (AUC_{0-tau}) (last SC dosing interval only) 	
 • Mean (SD) and geometric mean (geometric percent coefficient of variation [geometric %CV]) for all PK parameters except for T_{max} • Median (minimum, maximum) for T_{max}

Objectives	Endpoints and /or Estimand	Summary Measure(s)
1	Plasma PK parameters after the IV dose of CSL312: 
 • C_{max} • T_{max} • C_{trough} 	
 • Mean (SD) and geometric mean (geometric %CV) for all PK parameters except for T_{max} • Median (minimum, maximum) for T_{max}
2	Effect of treatment with CSL312 on activated coagulation factor XII (FXIIa) mediated kallikrein activity	
 • Mean (SD) change from Baseline in FXIIa-mediated kallikrein activity by treatment • Mean percentage of Baseline in FXIIa-mediated kallikrein activity by treatment
Exploratory		

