8.2.3 Baseline Definition

Baseline is defined as the most recent, non missing value before the first IP administration (including unscheduled visits) for all assessments unless otherwise stated.

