8.4 Study Periods Relative to Treatment

All data will be assigned to 1 of the 3 study time periods defined below.

- **Pre treatment** is defined as the time before the subject's first date / time of IP (Day 1).
- **On-treatment** (Treatment and Observation Period) is defined as the time from first date / time of IP up to Week 14 (Day 1 to Day 92).
- **Post treatment** begins after the end of the Treatment and Observation Period (Day 92) and continues through the Follow-up visit (follow-up telephone call) (Day 154).

9 Study Population

Unless otherwise stated, all tables and listings in this section will be based on the Safety Analysis Set.

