A laboratory value that is outside the reference range is either high abnormal (value above the upper limit of the normal [ULN] reference range) or low abnormal (value below the lower limit of the normal [LLN] reference range). An abnormal laboratory value is not necessarily of potential clinical interest. For each of the hematology and serum biochemistry lab tests, shift tables will be constructed to compare the individual subject baseline value with respect to the normal range to their Day 92 (or last observed value prior to Day 92 in case of dropouts or missing assessment at Day 92) value with respect to the normal range.

The denominator in percentage calculation at a scheduled visit will be based on the number of subjects with a non missing value at that particular visit. The definition of the baseline assessment is given in [Section 8.2.3](#).

A by-subject listing of all laboratory values including flag for values out of normal range will be provided. By-subject listing will include in general all visits (scheduled and unscheduled).

Immunogenicity:

The number and percentage of subjects with a positive immunogenicity test (presence of binding antibodies to CSL312) at any time and separate for Day 36 and Day 92 during treatment will be summarized by treatment group for the analysis population (Safety Analysis Set) as described in [Section 11](#).

A by-subject listing for immunogenicity will be provided.

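### The planned ADA table counts every positive test, so it does not measure the CSL312-induced ADA named in the primary endpoint

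*SAP*

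**What the plan says.** Protocol 2.1.2 lists "CSL312-induced ADAs" among the primary endpoint events, summarised for each arm as a count and proportion of subjects with the event after treatment. SAP Table 1 (section 4.1) repeats the component. Protocol 1.4.2 describes the risk in terms of change: "investigators will monitor subjects for the development of ADAs".

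The analysis text is different. Protocol 10.3.3 says only: "The number and percentage of subjects with plasma anti-CSL312 antibodies will be summarized by treatment group and overall". SAP 11.3 (Immunogenicity) plans a table by treatment group in the Safety Analysis Set. Its sole criterion for counting someone is a "positive immunogenicity test (presence of binding antibodies to CSL312) at any time and separate for Day 36 and Day 92 during treatment", and a by-subject listing goes with it.

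A baseline is available. The Schedule of Assessments places an ADA sample on Day 1, and its note P requires ADA samples before dosing. SAP 8.2.3 defines baseline as the "most recent, non missing value before the first IP administration (including unscheduled visits) for all assessments unless otherwise stated". The immunogenicity paragraph does not refer to it.

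**The concern.** An antibody is induced by a drug only if it was absent before the drug was given. The SAP table never looks at the pre-dose state, so a pre-existing antibody that persists to Day 36 or Day 92 is reported as an event. No other text supplies the condition: the baseline shift tables in SAP 11.3 cover hematology and serum biochemistry only. Adverse events, by contrast, have an explicit treatment-emergent rule in SAP 11.2, down to missing start dates.

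At stake is one labelled component of the primary endpoint in a study whose primary objective is safety. If any subject is positive on Day 1 and stays positive, the percentage reported under that label is too high. Working out induced ADA later from the listing would leave the definition, the denominator and the handling of a missing Day 1 result to be chosen after the data are seen.

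**Working it through.** **The plan's own figure.** The only related number is the sample size (Protocol 10.1, SAP 4.4). 70 / (1 − 0.12) = 79.5, rounded up to 80, or 40 per arm; 80 × 0.88 = 70.4. It reproduces. No ADA rate is stated in either document.

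**Can the wording be read as induced ADA?** There are two readings of the SAP 11.3 phrase.

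- If the words on treatment govern the whole phrase, SAP 8.4 starts that period at the first dose. The Day 1 pre-dose sample is then left out of the count, and a persistent positive is still counted at Day 36 or Day 92.
- If they govern only Day 36 and Day 92, a Day 1 positive counts by itself in the any-time row.

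Neither reading yields induced ADA. The any-time row is cumulative positivity, and the Day 36 and Day 92 rows are point prevalence. The denominator sentence in SAP 11.3 applies to a scheduled visit, so it does not settle the any-time row.

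**By subject counts.** Take an arm of 40 with all results available. Let k be the subjects positive on Day 1 and still positive on treatment, with no other Day 1 positives, and c the converters.

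- Planned = (k + c) / 40
- Induced = c / (40 − k)
- Gap = k(40 − k − c) / [40(40 − k)], which is positive whenever k > 0 and k + c < 40

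| k | c | Planned | Induced | Gap (points) |
|---|---|---|---|---|
| 0 | 1 | 1/40 = 2.5% | 1/40 = 2.5% | 0 |
| 1 | 0 | 1/40 = 2.5% | 0/39 = 0% | 2.5 |
| 1 | 1 | 2/40 = 5.0% | 1/39 = 2.6% | 2.4 |
| 2 | 1 | 3/40 = 7.5% | 1/38 = 2.6% | 4.9 |

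Each persistent positive adds 1/40 = 2.5 points to the planned figure, or 1/35 = 2.9 points on the Day 92 row if 35 subjects have a result.

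**By assumed rates.** Let b be Day 1 positivity, s the share of those subjects still positive on treatment, and i the incidence among Day-1-negative subjects. All three are assumptions. Expected planned proportion = b·s + (1 − b)·i. Expected induced proportion of all subjects = (1 − b)·i. The excess is b·s.

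- b = 5%, s = 100%, i = 2%: 0.05 + 0.95 × 0.02 = 6.9%, against 1.9%.
- b = 10%, s = 50%, i = 2%: 0.05 + 0.90 × 0.02 = 6.8%, against 1.8%.
- b = 0: the two are identical.

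Over b = 2% to 10% and s = 50% to 100%, the excess is 1 to 10 points. The chance of at least one Day 1 positive among 40 is 1 − (1 − b)^40: 55% at b = 2%, 87% at 5% and 98.5% at 10%.

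**Between arms.** With equal Day 1 positivity q and equal persistence in both arms, induction of 2.5% among Day-1-negative CSL312 subjects and none on placebo, the expected planned difference is (1 − q) × 2.5 points. That is 2.5 points at q = 0 and 2.25 at q = 10%.

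**The case against.** The strongest reply is that nothing in the documents shows the problem will arise. No baseline ADA rate is given, CSL312 is a fully human antibody, and exclusion criterion 11 bars prior CSL312 in another interventional study. With no Day 1 positives the table is exact. This stands as a limit on the size, but it does not make the rule measure what its label says.

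Second, the consequences are small. The placebo column shows background positivity, the arm difference hardly changes, there is no primary hypothesis (SAP 4.1.1), the halting criteria do not name ADA, and the by-subject listing would let a reader spot a persistent Day 1 positive. All of this is true, and it keeps the point below a critical fault. But a placebo column does not classify individual subjects, and a listing is not a pre-specified estimate.

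Third, SAP 11.3 follows Protocol 10.3.3, so the mismatch begins inside the protocol. That is correct. The SAP is still where the definition belongs.

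Fourth, a negative-to-positive rule cannot credit a boosted response in a subject already positive on Day 1, and it applies the label CSL312-induced to placebo converters. The documents describe testing for the presence of antibodies and mention no titre, so showing Day 1 positives as a separate count is an adequate answer on boosting. Applying the flag in both arms follows the protocol's own summary measure, which names both products.

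**Conclusion.** The concern holds. Followed as written, SAP 11.3 reports on-treatment antibody positivity under a primary endpoint component that is named as induced antibody. The overstatement is 2.5 percentage points per persistent Day 1 positive in an arm of 40, measured against the planned denominator. It is zero if there are none. The direction follows from the definition alone. The size depends on a Day 1 positivity rate that the documents do not give. The effect on the between-arm comparison is minor. This should be corrected before database lock, but it does not threaten the study's conclusions.

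**What to change.** In SAP 11.3:

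- Define CSL312-induced ADA as a negative Day 1 pre-dose result (baseline as in SAP 8.2.3) followed by at least one positive post-dose result.
- Report the number and percentage by arm among Safety Analysis Set subjects who were negative on Day 1 and have at least one post-dose result. For the Day 36 and Day 92 rows, use Day-1-negative subjects with a result at that visit.
- Show Day-1-positive and Day-1-missing subjects as separate counts by arm.
- State that the any-time row uses post-dose samples only.
- Keep the any-positive percentage as a supportive row, labelled as such.

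The cost is a few lines of text and one derived flag, with no new samples or assays. The denominator shrinks slightly: 39 of 40 with one Day 1 positive and 38 with two, before missing results. SAP version 1.0 is based on the protocol only through Amendment 2, and its section 7.1 still treats COVID-19 vaccination as excluded although Amendment 3 permits it. An SAP update is therefore needed anyway and can carry this change.

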11.4 Other Safety Measures

11.4.1 Vital Signs

The vital signs will be summarized by visit and by treatment group. The summaries will be provided for the analysis population (Safety Analysis Set) as described in [Section 11](#).

The following summaries will be provided for systolic and diastolic blood pressure, heart rate, respiratory rate, body temperature, weight, and BMI:

- Values of vital signs by scheduled visit,
- Change from baseline by scheduled visit.

The position of vital sign measurement and the location of body temperature measurement will be not included in the summaries, ie the summaries will be not provided by position or location.

A by-subject listing of all vital sign data (scheduled and unscheduled visits) will also be presented. The by-subject listing will include a flag for values of potential clinical importance.

11.4.2 Electrocardiogram (ECG)

The ECG parameter (PR interval, QRS duration, QT interval, QTcB, QTcF, and heart rate) and their changes from baseline will be summarized by visit and by treatment group. The

summaries will be provided for the analysis population (Safety Analysis Set) as described in [Section 11](#).

A by-subject listing of all ECG data (scheduled and unscheduled visits) will also be presented. The by-subject listing will include a flag for values of potential clinical importance.

11.4.3 Diffusing Capacity of the Lungs for Carbon Monoxide (DLCO)

DLCO and its changes from baseline will be summarized by visit and by treatment group. The summary will be provided for the analysis population (Safety Analysis Set) as described in [Section 11](#).

A by-subject listing for DLCO data (scheduled and unscheduled visits) will also be presented.

11.4.4 Physical Examination

Abnormalities of physical examination reported at screening will be recorded as medical history. Abnormalities of physical examination reported at other visit will be recorded as an AE.

12 Pharmacokinetic Analyses

All noncompartmental analyses are to be performed using CSL312 plasma concentrations according to CSL SOP [PK-GDL-01](#) and will be performed by ICON, under the direction of CSL Behring Clinical Pharmacology and Pharmacometrics, by using WinNonLin® version 8.0 or later.

The merge of PK concentration data and CRF data to generate SDTM domain PC with nominal blood sampling times, actual blood sampling time relative to dosing, actual dosing, and CSL312 plasma concentrations will be performed after DBL by Parexel. Parexel will produce the SDTM PC domain needed by ICON for PK parameter derivation.

ICON, under the direction of CSL Behring Clinical Pharmacology and Pharmacometrics, will derive the individual PK parameters and will provide them to Parexel. From this, Parexel will produce the SDTM domain PP and will generate the analysis dataset. Any CSL312 plasma concentrations which have been excluded from the derivation of the PK parameters will be flagged by ICON in SDTM PC domain and provided to Parexel.

All analyses in this section will be based on the PK Analysis Set.

12.1 Drug Concentration Measures

Handling of PK concentration data and imputation of below limit of quantification (BLQ) values for non compartmental analyses will be performed according to [PK-GDL-01](#). The imputation rules below will be used for summary statistics of CSL312 plasma concentrations. The summaries will be given by nominal (planned) time point.

- The sampling time of pre dose samples relative to start of the dose will be treated as zero;
- Concentration values that are BLQ in pre dose samples and in samples taken before the time of the first quantifiable concentration will be treated as zero;
- Post dose BLQ concentrations flanked by quantifiable concentrations will be set to missing;
- If 2 or more BLQ concentrations occur in succession, the profile will be considered to have terminated at the quantifiable concentration prior to the 2 consecutive BLQs. All subsequent values will be treated as missing;
- Post dose BLQ concentrations after the last quantifiable point will be set to missing for summary statistics of plasma concentrations;
- The mean/median value at a time point where 1 or more samples have BLQ values will be reported (in tabular or graphical fashion) even if the mean/median value is BLQ of the assay;
- Zero mean or median values will be included in summary tables.

The lower limit of quantification for CSL312 in plasma is 100.0 ng/mL. Concentrations that are below BLQ should be reported as “< LLOQ” in by-subject listings.

Summary statistics for CSL312 plasma concentration-time data will be presented as follows: number of observations (n), mean, SD, %CV (CV% = 100* standard deviation / mean), median, geometric mean, geometric %CV, minimum, and maximum.

$$\text{Geometric CV\%} = 100 * \sqrt{\exp(SD^2) - 1}.$$

In addition, summary statistics will also include the percentage of BLQ values relative to the total number of observations:

$$\% \text{ BLQ} = 100 * (\text{number of subjects who have BLQ values} / \text{total number of subjects at each time point}).$$

It should be noted that a high proportion of BLQ values may affect the summary statistics; if more than 50% of the values are imputed (i.e. BLQ), then the summary statistics (mean, SD, median, quartiles) will not be displayed.

Individual CSL312 plasma concentration-time profiles (on linear and log-linear scale) will be plotted using actual sampling time.

Plots for mean (\pm SD) CSL312 plasma concentration-time profiles (on linear and log-linear scale) will be plotted using nominal (planned) time.

A by-subject listing of CSL312 plasma concentrations with the concentrations flagged that have been excluded from the derivation of the PK parameters based on the PK Analysis Set will support the summaries.

12.2 Deriving and Summarizing Pharmacokinetic Parameters

For subjects belonging to the PK Analysis Set, the PK parameters provided in [Appendix 15.1](#) will be determined, if applicable, from plasma concentration-time data for CSL312.

The PK parameter derivation including imputation of the values BLQ and missing data will be conducted in accordance to [PK-GDL-01](#) which gives guidance on how to derive PK parameters in the presence of missing data. The PK parameters will be calculated by standard non-compartmental analysis using actual sampling times and actual doses.

The following PK parameters will be summarized after SC administration of CSL312 at each SC dosing interval:

Variable	Statistical Parameters:
C _{trough} after first, second and third SC dose; C _{max} after last SC dose; AUC _{0-tau} after last SC dosing interval	n, arithmetic mean, SD, CV%, minimum, median, maximum, geometric mean and geometric CV%
T _{max} after last SC dose	n, minimum, median, and maximum

The following PK parameters will be derived and summarized after the IV administration of CSL312:

Variable	Statistical Parameters:
C _{max} C _{trough}	n, arithmetic mean, SD, CV%, minimum, median, maximum, geometric mean and geometric CV%
T _{max}	n, minimum, median, and maximum

All PK parameters will be reported to at least 3 significant digits, but to no more significant digits than the precision of the original data.

A by-subject listing of CSL312 PK parameters based on the PK Analysis Set will be provided.

13 Pharmacodynamic and Biomarkers Analyses

Unless otherwise specified, analyses in this section will be based on the PD Analysis Set.

13.1 Pharmacodynamic Analyses

The absolute change from baseline in FXIIa-mediated kallikrein activity over time will be calculated for each subject. The comparison of primary interest is the change from baseline at Day 92 (Week 14). The change from baseline will be compared between CSL312 and placebo using a mixed-model repeated measure (MMRM) analysis, with treatment group and visit as fixed effects, and baseline as a covariate. Interactions with visit will be included for treatment group and baseline. The analysis will be implemented by using SAS PROC MIXED. A restricted maximum likelihood (REML) approach will be used. An unstructured variance-covariance structure will be used to model the within-subject errors. This variance-covariance matrix will be estimated across treatment groups. If the model fails to converge, a heterogeneous Toeplitz structure (the TOEPH option in SAS PROC MIXED) will be used. The Kenward-Roger approximation will be used to estimate denominator degrees of freedom and adjust standard errors. Mean difference in least square means (LSMeans) between treatment groups and its 95% confidence interval will be provided at each time point, assuming that the data is normally distributed. If the data are not normally distributed by visual inspection of residual plots (QQ plots), an appropriate data transformation, log transformation, may be done.

FXIIa-mediated kallikrein activity will be summarized by nominal time point with the following descriptive statistics: n, mean, SD, %CV, minimum, Q1, median, Q3, maximum, geometric mean, geometric %CV, and percent below the limit of quantification (% BLQ).

Individual observed FXIIa-mediated kallikrein activity-time profiles will be plotted using actual sampling times. Mean (\pm SD) observed FXIIa-mediated kallikrein activity-time profiles will be plotted by using nominal (planned) time points.

The absolute change from baseline, percent change from baseline, and percent of baseline of FXIIa-mediated kallikrein activity over time will be summarized using descriptive statistics as done for the observed values of FXIIa-mediated kallikrein activity. The absolute change from baseline and percent of baseline of FXIIa-mediated kallikrein activity will also be presented graphically by treatment group as done for the observed FXIIa-mediated kallikrein activity.

Other observed PD parameter of FXII concentration will be summarized by nominal time point by descriptive statistics (n, mean, SD, %CV, minimum, Q1, median, Q3, maximum, geometric mean, geometric %CV). The absolute and percent change from baseline for those PD parameters will also be summarized by nominal time point by descriptive statistics. For all PD parameters, including aPTT, the absolute changes from baseline will be analyzed by the MMRM as described for FXIIa-mediated kallikrein activity.

Individual observed PD parameter time profiles will be plotted using actual sampling times. Mean (\pm SD) observed PD parameter time profiles will be plotted by using nominal (planned) time points.

A by-subject listing of PD parameters including observed values, absolute and percent change from baseline will be provided.

